6. STUDY CALENDAR

Neoadjuvant Calendar:

Evaluation	Initial Screen ⁴ ≤28d prior to 1 st cycle	Patient Enrolled (0 Day)	Week 1 Neoadjuvant cycle 1 (±3d)	Week 4 Neoadjuvant cycle 2 (±3d)	Week 6 Post-neo-adjuvant: Imaging & Safety (±10d)	Surgery ¹
Inclusion/Exclusion Criteria	X					
Demographics	X					
Medical History	X					
Weight and Vital Signs	X		X	X	X	
Atezolizumab			X	X		
MRI or CT Head and Neck	X				X	
PET	X					
Blood Collection ⁵	X		X	X	X	X
Tissue Collection ⁵	X					X
Physical Exam	X		X	X	X	
Urinalysis	X					
Pregnancy Test	X					
Adverse Events			X	X		X

Adjuvant Calendar: Patient with pCR at time of surgery

Evaluation	Post-surgery Visit 1 week (±3d)	Post-surgery Visit 1 month (±14d)	Surveillance Follow Up Every 3 mo to 3 years (±14d)
Inclusion/Exclusion Criteria			
Demographics			
Medical History			
Weight and Vital Signs	X	X	X
Atezolizumab			
MRI or CT Head and Neck			
PET			X ²
Blood Collection ⁵			X
Tissue Collection ⁵			
Physical Exam	X	X	X
Pregnancy Test			
Adverse Events	X	X	

Adjuvant Calendar: Patient with residual disease at time of surgery

Evaluation	Post-surgery Visit 1 week ($\pm 3d$)	Post-surgery Visit 1 month ($\pm 14d$)	Adjuvant Cycle #1 ⁶ < 7 wks post-op		Adjuvant Cycle #2 +3W ($\pm 3d$)		Adjuvant Cycles #3 - #15 +3W ($\pm 3d$)	Surveillance Follow Up Every 3 mo to 3 yr ³ ($\pm 14d$)
			Weeks					
			1	2	3	4	5	6
Inclusion/Exclusion Criteria								
Demographics								
Medical History								
Weight and Vital Signs	X	X	X		X		X	X
Atezolizumab			X		X		X	
MRI or CT Head and Neck								
PET								X ²
Blood Collection ⁵			X		X		X	X
Tissue Collection ⁵								
Physical Exam	X	X	X		X		X	X
Urinalysis								
Pregnancy Test			X		X		X	
Adverse Events	X	X	X		X		X	X ⁷
Atezolizumab 1200 MG			X		X		X	
Adjuvant Radiation			X X X X X X					

1. Surgery must be completed within 10 weeks after patient is enrolled.
2. Only performed at 3mo follow up visit per standard of care.
3. If the patient is unable to attend the standard of care office appointment they will be contacted via video or phone visit.
4. Any screening assessments performed within 28 days prior to the consent signing can be accepted.
5. See section 5.1.5.
6. Start adjuvant therapy more than 4 weeks after and within 7 weeks after surgery per SOC.
7. AE monitoring at first surveillance visit only ≥ 30 days following last dose of Atezolizumab

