2.2 Secondary Objectives

1) Further characterize the oncologic response to neo-adjuvant atezolizumab and adjuvant atezolizumab in combination with radiation therapy in patients with regionally metastatic HNSCCC:

- a) Determine the rate of major pathologic response (mPR) at the time of surgery.
- b) Evaluate the 2-year event free survival (EFS) after completion of adjuvant therapy.

2) Investigate the utility of conventional imaging and novel biomarkers in predicting and assessing response to neoadjuvant atezolizumab therapy.

- a) Investigate associations between pre-treatment tumor FDG avidity and response to neoadjuvant immunotherapy

- b) Evaluate the ability of fine-cut contrast enhanced CT or MRI of the head and neck to assess response to neoadjuvant immunotherapy prior to surgery.
- c) Evaluate the capabilities of serial liquid biopsy analysis of tumor-associated exosomes to predict neoadjuvant immunotherapy response.

3) Evaluate the safety and tolerability of anti-PD-L1 with atezolizumab neo-adjuvant therapy in resectable regional metastatic HNCSCC.

- a) Quantify Toxicity (adverse events) determined by CTCAE v5

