Because of the possibility of an initial increase in tumor burden caused by immune cell infiltration in the setting of a T-cell response (termed pseudoprogression) with atezolizumab treatment, clinical or radiographic progression per iRECIST may not be indicative of true disease progression. In the absence of unacceptable toxicity, patients with clinical or radiographic evidence of progression while receiving neo-adjuvant atezolizumab will be permitted to receive their second dose and postoperative adjuvant doses of atezolizumab if they meet all of the following criteria:

- Evidence of clinical benefit, as determined by the investigator following a review of all available data
- Absence of symptoms and signs (including laboratory values, such as new or worsening hypercalcemia) indicating unequivocal progression of disease
- Absence of decline in Performance Status that can be attributed to disease progression
- Absence of tumor progression at critical anatomical sites (e.g., leptomeningeal disease) that cannot be managed by protocol-allowed medical interventions

Patient who have NOT met all of the above criteria will NOT receive their second dose of neo-adjuvant atezolizumab and will proceed directly to surgery. These patients will also not receive adjuvant atezolizumab and will receive only SoC adjuvant radiation.

Pre-Dose Blood Draws

Participants will undergo blood draws at the infusion center prior to administration of neo-adjuvant atezolizumab for routine blood analysis as noted in section 5.1.5. One 4 mL lavender-top tube will be drawn simultaneously with these scheduled blood draws for research analysis of tumor-associated exosomes. This research vial will be transported by [name], [name], [name], or other approved Otolaryngology department members to the Cancer Center Biorepository for cataloging (contact: [name]), and storage as needed. Collected whole blood samples will be withdrawn and processed by [name] and collaborators when needed for subsequent analysis.

Post-neo-adjuvant Imaging

Repeat fine-cut contrast-enhanced CT or MRI imaging of the head and neck will be performed one week prior to surgery to assess response to neo-adjuvant therapy. The imaging modality utilized will be the same as that modality used for screening.

Surgery and Pathologic Evaluation

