4.3 Inclusion of Women, Minorities, and Other Underrepresented Populations

Recruitment is open to all minorities and both genders. Although distributions may vary by disease type, our recruitment procedures have been developed to enroll patients who are representative of the respective target population.

5. STUDY EVALUATIONS**5.1 Study Assessments**

The schedule of activities to be performed during the study is provided in section 6. All activities must be performed and documented for each patient. Patients will be closely monitored for safety and tolerability throughout the study. Patients should be assessed for toxicity prior to each dose; dosing will occur only if the clinical assessment and local laboratory test values are acceptable.

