9.4.1 Adverse Event Reporting Period

The study period during which all AEs and SAEs must be reported beginning at initiation of study treatment until 30 days following the last administration of study treatment or study discontinuation/termination, whichever is earlier. After this period, investigators should only report SAEs that are attributed to prior study treatment.

Investigators will seek information on adverse events at each patient contact. All adverse events, whether reported by the patient or noted by study personnel, will be recorded in the patient's medical record.

Assessment of Adverse Events

All AEs and SAEs whether volunteered by the patient, discovered by study personnel during questioning, or detected through physical examination, laboratory test, or other means will be reported appropriately. Each reported AE or SAE will be described by its duration (i.e., start and end dates), regulatory seriousness criteria if applicable, suspected relationship to atezolizumab (see following guidance), and actions taken.

To ensure consistency of AE and SAE causality assessments, investigators should apply the following general guideline:

Yes

There is a plausible temporal relationship between the onset of the AE and administration of atezolizumab, and the AE cannot be readily explained by the subject's clinical state, intercurrent illness, or concomitant therapies; and/or the AE follows a known pattern of response to atezolizumab or with similar treatments; and/or the AE abates or resolves upon discontinuation of atezolizumab or dose reduction and, if applicable, reappears upon re-challenge.

No

Evidence exists that the AE has an etiology other than atezolizumab (e.g., preexisting medical condition, underlying disease, intercurrent illness, or concomitant medication); and/or the AE has no plausible temporal relationship to atezolizumab administration (e.g., cancer diagnosed 2 days after first dose of atezolizumab).

Expected adverse events are those adverse events that are listed or characterized in the Package Insert (P.I) or current Investigator Brochure (I.B).

Unexpected adverse events are those not listed in the P.I. or current I.B or not identified. This includes adverse events for which the specificity or severity is not consistent with the description in the P.I. or I.B. For example, under this definition, hepatic necrosis would be unexpected if the P.I. or I.B. only referred to elevated hepatic enzymes or hepatitis.

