9.5 Procedures for Eliciting, Recording, and Reporting Adverse Events

9.5.1 Eliciting Adverse Event Information

A consistent methodology of non-directive questioning should be adopted for eliciting adverse event information at all patient evaluation timepoints. Examples of non-directive questions include the following:

"How have you felt since your last clinic visit?"

"Have you had any new or changed health problems since you were last here?"

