10.3 Evaluation of Safety

Safety and tolerability will be assessed through detailed history and physical at each clinical visit and documented using CTCAE v5. In addition, patients will complete EORTC QLQ-C30 and EORTC QLQ-H&N35 surveys at each clinic visit.

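### Minor: the neoadjuvant calendar has no pregnancy test at dose 2 and no Adverse Events tick at the Week 6 safety visit

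*Combined protocol and SAP*

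**What the plan says.** Section 5.1 gives the calendar its standing: "The schedule of activities to be performed during the study is provided in section 6", followed by "All activities must be performed and documented for each patient".

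**Pregnancy testing.** The neoadjuvant calendar ticks this row at the initial screen and nowhere else. The calendar for patients with residual disease ticks it in each atezolizumab column: cycle 1, cycle 2 and cycles 3 to 15. Section 3.3.2 gives the same 1200 mg three-weekly regimen in both settings. Section 5.1.5 places the pregnancy test in the list of tests for screening and every follow-up visit, subject to exceptions stated elsewhere. It then asks for a serum test at screening and urine tests at later visits that are to be specified. Section 5.3 lists pregnancy among the reasons for permanent discontinuation.

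**Adverse events.** The neoadjuvant Adverse Events row is ticked at Week 1, Week 4 and Surgery. It is blank at "Week 6 Post-neo-adjuvant: Imaging & Safety", where vital signs, head and neck imaging, blood collection and physical examination are all ticked. The text rules are broader:

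- Section 9.4.1: "Investigators will seek information on adverse events at each patient contact".
- Section 9.5.1: a consistent method of questioning "should be adopted for eliciting adverse event information at all patient evaluation timepoints".
- Section 10.3: "Safety and tolerability will be assessed through detailed history and physical at each clinical visit and documented using CTCAE v5".

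The third secondary objective in section 2.2 is to "Evaluate the safety and tolerability of anti-PD-L1 with atezolizumab neo-adjuvant therapy in resectable regional metastatic HNCSCC".

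**The concern.** Site staff usually work from the calendar cells. A site doing so here would give dose 2 on the strength of a screening pregnancy test that may be weeks old, yet would test before every adjuvant dose of the same treatment. The plan gives no reason for the difference. What is at stake is a second dose given during an undetected pregnancy, when the plan itself would require treatment to stop.

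The same site would find no prompt to ask about adverse events at the visit named for safety, which follows dose 2 and precedes the operation. The safety of the neoadjuvant doses is a stated secondary objective, so the table should prompt the inquiry that the text requires.

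**Working it through.** The plan states no figure on this point, so there is none to reproduce. The check is a reading of the calendar cells against the text, plus day counts.

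**1. Are the blanks real?** The neoadjuvant calendar has six columns: Initial Screen, Enrolled, Week 1, Week 4, Week 6 and Surgery. The Adverse Events row has a further tick after the Week 6 blank, at Surgery, and the other rows line up on the same six columns. The blank is therefore not a shifted column. The pregnancy row has one tick, at screening.

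**2. Age of the last scheduled pregnancy test at dose 2.**

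- Screening window: up to 28 days before cycle 1 (calendar header).
- Dose 1 to dose 2: 21 days (section 3.1).
- Age at dose 2: 28 + 21 = 49 days.
- With the +3-day window on the Week 4 visit: 49 + 3 = 52 days.

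Neither figure is a firm maximum. Footnote 4 to the calendar accepts screening assessments from up to 28 days before consent is signed. Where consent precedes dose 1 by some days, an accepted test could be older still. The documents do not fix that interval, so I read the result as about 49 days or longer. In the residual-disease calendar the test falls in the same column as each dose. A test at neoadjuvant cycle 2 would likewise place it at the dosing visit.

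**3. Adverse event checks by the ticks alone.** Assume each week is counted at its first day: dose 2 is day 22 and Week 6 is day 36. Section 3.1 says repeat "imaging of the head and neck will be performed one week prior to surgery to assess response to neo-adjuvant therapy", so surgery is taken as 36 + 7 = day 43.

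| | Days from dose 2 to next ticked check |
|---|---|
| As ticked (Surgery) | 43 − 22 = 21 |
| With Week 6 ticked | 36 − 22 = 14 |

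These are nominal values. The windows of ±3 days on dose 2 and ±10 days on Week 6 move both. They describe the table only, since the text already requires an earlier inquiry.

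**4. Table against text.** The Week 6 visit includes an examination and vital signs. It is therefore a patient contact (9.4.1), an evaluation timepoint (9.5.1) and a clinical visit (10.3). All three rules reach it, and the Adverse Events cell does not reflect them.

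**The case against.** The strongest reply is that nothing is actually missing. Section 5.1 says that the calendar's activities must be done; it does not say that nothing else may be. A blank cell prohibits nothing, and three text rules already require the Week 6 inquiry. This stands, and it reduces the adverse event part to an alignment edit.

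On pregnancy testing, two doses three weeks apart are a shorter exposure than 15 adjuvant cycles, and section 4.1 already requires abstinence or effective contraception. The list in 5.1.5 could also be read as covering the dose 2 visit. Part of this stands: contraception lowers the risk, and 5.1.5 can be read in more than one way. But 5.1.5 leaves urine tests to specified visits, and the neoadjuvant calendar specifies none. That ambiguity is a reason to fill the cell.

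Three stronger readings are tempting, and the documents do not support them:

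- A reader might infer that Week 6 is the only visit scheduled between dose 2 and surgery. Section 5.1.4 calls for tumor assessments every two weeks up to surgery. Week 6 is only the sole calendar column in that interval.
- A reader might infer that adverse events would go unrecorded or fall outside the 30-day reporting period. Section 9.3 records start and stop dates, and the calendars tick Adverse Events at surgery and at one week and one month afterwards. A late inquiry can still capture an earlier event.
- A reader might infer that the calendar breaches a three-weekly testing rule in 5.1.5. That sentence is conditional on the class of product and does not name atezolizumab.

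**Conclusion.** The point holds as a minor, inexpensive improvement. The pregnancy test is the part that changes what is done: dose 2 can be given about 49 days or more after the last scheduled test, although the plan tests at every adjuvant dose. The conflict is between one calendar and another, with 5.1.5 leaning toward testing without clearly requiring it. The documents do not give the number of women of childbearing potential among the 18 planned patients, so the number affected is unknown.

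The blank Adverse Events cell is a mismatch between table and text. Its practical effect depends on a site following the cells and overlooking 9.4.1, 9.5.1 and 10.3. Neither gap touches the pathologic complete response endpoint, the two-stage decision rule or the sample size.

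**What to change.** Make two edits to the neoadjuvant calendar in section 6:

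1. Tick Pregnancy Test at Week 4 (neoadjuvant cycle 2), with a note that it is a urine test for women of childbearing potential, confirmed by serum if positive as 5.1.5 already provides.
2. Tick Adverse Events at Week 6.

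The first adds one urine test per eligible woman at a visit that already takes place. The second adds no procedure, because the text already requires the inquiry. No new visit, analysis or change in sample size is needed.

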All participants will undergo a curative-intent surgical resection as defined by SoC. Surgery will occur within 10 weeks of study enrollment and at least two weeks after second dose of neoadjuvant Atezolizumab. The goal of curative intent surgery for regionally metastatic CSCC involves resection to negative margins of the index lesion with the associated at-risk regional lymph nodes as determined by the study physician. An evaluation of tumor status and staging per AJCC guidelines (8th edition) will be performed on all surgical specimen. The pathologist will assess the specimen for pCR and mPR (see 10.1). Pathology assessment will be as per standard of care documentation, including: dimensions of index lesion, total nodal number of lymph nodes removed, total positive node number (and positive nodal levels), any extracapsular extension, any perineural invasion. PD-L1 staining will be performed on a representative section from the largest positive node. Tissue will be formalin fixed and paraffin embedded and banked per standard pathology protocol.

Patients demonstrating pCR at time of surgery:*Adjuvant Treatment*

Patients demonstrating pCR at the time of surgery will not receive any additional adjuvant therapy and will enter surveillance.

Imaging

PET/CT will be performed approximately 12 weeks after surgery.

Follow-up / Surveillance

Patients will be followed in otolaryngology/head and neck surgery and medical oncology clinic every 3 months for 3 years after surgery. Patients will be assessed for treatment-related side effects, cancer recurrence and blood draws performed at the cancer center for biomarkers.

In the setting of suspected clinical or radiographic recurrence per iRECIST criteria, tumor tissue will be collected by biopsy, unless not clinically feasible as assessed and documented by the investigator.

Patients with residual disease at time of surgery:

Patients with residual disease at the time of surgery will receive atezolizumab Q3W x 15 cycles in combination with SoC adjuvant radiation. SoC adjuvant radiation will be initiated greater than 4 weeks and less than 7 weeks after surgery and consists of 6 weeks of radiation therapy with dosimetry determined by pathologic findings at the time of surgery. Recommendations for adjuvant treatment will be determined at a multidisciplinary tumor board where surgical pathology findings will be reviewed. Adjuvant atezolizumab will begin concurrent to adjuvant radiation and continue for 15 cycles.

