Pre-Dose Blood Draws

As in the neo-adjuvant setting, participants will undergo blood draws at the infusion center prior to administration of adjuvant atezolizumab for routine blood analysis as noted in section 5.1.5. One 4 mL lavender-top tube will be drawn simultaneously with these scheduled blood draws for research analysis of tumor-associated exosomes. This research vial will be transported by [name], [name], [name], or other approved Otolaryngology department members to the Cancer Center Biorepository for cataloging (contact: [name]), and storage as needed. Collected whole blood samples will be withdrawn and processed by [name] and collaborators when needed for subsequent analysis.

Imaging

All participants will have imaging performed with PET/CT approximately 12 weeks after completion of adjuvant RT.

Follow-up / Surveillance

Patients will be followed in otolaryngology/head and neck surgery and medical oncology clinic every 3 months for 2 years after completion of adjuvant atezolizumab. Patients will be assessed for treatment-related side effects, cancer recurrence and blood draws for biomarker. In the setting of suspected clinical or radiographic recurrence per iRECIST, tumor tissue will be collected by biopsy, unless not clinically feasible as assessed and documented by the investigator.

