4.1 Inclusion Criteria

Patients must meet all of the following criteria to be eligible for study entry.

1. Patients must be \geq 18 years
2. Patients with resectable regionally metastatic HNCSCC from an unknown or historical primary and no evidence of distant metastatic disease.
3. Full decision-making capacity and consent provided and documented.
4. Radiographically measurable disease per iRECIST
5. Surgically resectable disease per SoC.

6. For Women of childbearing potential: agreement to remain abstinent (refrain from heterosexual intercourse) or use contraceptive methods as defined below:
 - Women must remain abstinent or use contraceptive methods with a failure rate of < 1% per year during the treatment period and for 5 months after the final dose of atezolizumab.
 - A woman is considered to be of childbearing potential if she is postmenarchal, has not reached a postmenopausal state (≥ 12 continuous months of amenorrhea with no identified cause other than menopause), and has not undergone surgical sterilization (removal of ovaries and/or uterus). The definition of childbearing potential may be adapted for alignment with local guidelines or requirements.
 - Examples of contraceptive methods with a failure rate of < 1% per year include bilateral tubal ligation, male sterilization, hormonal contraceptives that inhibit ovulation, hormone-releasing intrauterine devices, and copper intrauterine devices.
 - The reliability of sexual abstinence should be evaluated in relation to the duration of the clinical trial and the preferred and usual lifestyle of the patient. Periodic abstinence (e.g., calendar, ovulation, symptothermal, or postovulation methods) and withdrawal are not adequate methods of contraception.
7. Men: abstinent or using effective contraception method
8. Tumor tissue sample adequate for PD-L1 and biomarker studies
9. ECOG performance status 0 or 1 (Section 15.1).
10. Availability of a representative tumor specimen for exploratory biomarker research (see Section 5.1.5 for information on tumor specimens)
11. Life expectancy ≥ 2 years
12. Adequate hematologic and end-organ function, defined by the following laboratory test results, obtained within 14 days prior to initiation of study treatment:
 - ANC $\geq 1.5 \times 10^9/L$ (1500/ μ L) without granulocyte colony-stimulating factor support
 - Lymphocyte count $\geq 0.5 \times 10^9/L$ (500/ μ L)
 - Platelet count $\geq 50 \times 10^9/L$ (50,000/ μ L) without transfusion

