9.1 Adverse Event Definition

Any patient enrolled in the trial who signed the consent form and received at least one dose of atezolizumab will be eligible for adverse event reporting. Only laboratory abnormalities that result in signs or symptoms that require intervention or follow up and are considered clinically significant should be recorded as AEs. All other AEs whether serious or non-serious will be entered into the institutional database from the time of first protocol intervention up until 30 days after the last dose of study drugs. The Principal Investigator or designee will be responsible for assigning attribution to the study treatment.

This includes the following:

- AEs not previously observed in the subject that emerge during the protocol-specified AE reporting period, including signs or symptoms associated with squamous cell carcinoma that were not present prior to the AE reporting period.
- Complications that occur as a result of protocol-mandated interventions (e.g., invasive procedures such as cardiac catheterizations)
- If applicable, AEs that occur prior to assignment of study treatment associated with medication washout, no treatment run-in, or other protocol-mandated intervention.
- Preexisting medical conditions (other than the condition being studied) judged by the

investigator to have worsened in severity or frequency or changed in character during the protocol-specified AE reporting period.

The descriptions and grading scales found in the revised NCI Common Terminology Criteria for Adverse Events (CTCAE) version 5.0 will be utilized for AE reporting. All appropriate treatment areas should have access to a copy of the CTCAE version 5.0. A copy of the CTCAE version 5.0 can be downloaded from the CTEP web site

http://ctep.cancer.gov/protocolDevelopment/electronic_applications/ctc.htm.

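### The sections conflict on how long non-serious adverse events are collected; if the 30-day rule governs, late non-serious toxicity is under-reported

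*Combined protocol and SAP*

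**What the plan says.** Two places have toxicity assessed throughout surveillance.

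- Section 3.1, pCR patients: seen "every 3 months for 3 years after surgery", with this content: "Patients will be assessed for treatment-related side effects, cancer recurrence and blood draws performed at the cancer center for biomarkers".
- Section 3.1, residual-disease patients: seen "every 3 months for 2 years after completion of adjuvant atezolizumab", with this content: "Patients will be assessed for treatment-related side effects, cancer recurrence and blood draws for biomarker".
- Section 10.3, on the evaluation of safety, has toxicity documented by CTCAE v5 at each clinical visit and names no end date.

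Three places stop much earlier.

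- Section 9.1 has adverse events entered in the institutional database "up until 30 days after the last dose of study drugs".
- Section 9.4.1 sets the same 30 days and adds: "After this period, investigators should only report SAEs that are attributed to prior study treatment". Section 9.5.2.6 adds all deaths to what is reported after that point.
- Section 6: the adverse-event row of the pCR calendar is marked at 1 week and 1 month after surgery and is blank in the surveillance column. In the residual-disease calendar, footnote 7 limits the surveillance mark to "AE monitoring at first surveillance visit only", at 30 days or more after the last dose.

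Section 10.1 describes the toxicity analysis and its tiers. It does not say which period the analysis covers.

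**The concern.** Safety and tolerability of neoadjuvant atezolizumab is secondary objective 3, and CTCAE toxicity is its endpoint. The tables will be built from whatever reaches the database. Clinicians are told to look for treatment-related effects for 2 to 3 years, while the reporting section tells data staff to stop after 30 days unless the event is serious and related. A site that follows section 9 would leave non-serious immune-mediated events of late onset out of the endpoint; a site that follows 10.3 would include them. With 18 patients, a few such events would visibly change the reported rate, and a reader of the results could not tell which rule had been applied.

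**Working it through.** The plan states no figure on this point to reproduce. The check is a comparison of rules plus simple timing arithmetic.

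**1. Surveillance visits with an adverse-event mark (sections 3.1 and 6)**

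- pCR: 36 months / 3 = 12 visits, 0 marked.
- Residual disease: 24 / 3 = 8 visits under section 3.1, 1 marked. The calendar heads the same column as running to 3 years, which would make it 1 of 36 / 3 = 12.

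**2. Timing of the marked visits against day 30**

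Assumptions: dose 1 on day 1 at enrollment, dose 2 on day 22, 1 month = 30 days, 3 months = 91 days, dosing windows ignored. Section 3.1 puts surgery at least 2 weeks after dose 2 and within 10 weeks of enrollment, so between day 22 + 14 = 36 and day 70.

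- pCR, 1-month post-surgery visit (±14 days): earliest 36 + 30 − 14 − 22 = 30 days after dose 2; latest 70 + 30 + 14 − 22 = 92 days. It never falls before the cut-off. The lower figure needs only the two-week minimum; the upper one also needs dose 1 at enrollment.
- pCR, 1-week visit (nominal): 36 + 7 − 22 = 21 to 70 + 7 − 22 = 55 days after dose 2, so it can fall on either side.
- pCR, first surveillance visit: no earlier than 36 + 91 − 14 − 22 = 91 days after dose 2, and unmarked.
- Residual disease, first surveillance visit: 91 ± 14 = 77 to 105 days after the last dose, and marked.

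So the calendar conflicts with section 3.1, and it also schedules adverse-event visits after the date on which section 9.1 closes entry.

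**3. One event followed through the rules**

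Take symptomatic, non-serious hypothyroidism, first arising 60 days after dose 2 in a pCR patient. Hypothyroidism is on the risk list in 5.2.1.

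- Section 9.4.1 has it sought at patient contact and written in the medical record.
- Section 9.1: entry closed at day 30.
- Section 9.4.1 after day 30: not serious, so not reported.
- Section 9.3.1, events of special interest: thyroid, adrenal and pituitary events are not listed, nor is non-severe rash. Listed events go to the drug supplier's safety group.
- Laboratory shifts (5.1.5, 10.1): thyroid tests are specified at screening, neoadjuvant cycle 2 and alternate adjuvant cycles, not in surveillance.
- Sections 9.3 and 10.3 would have it recorded, but neither says that it overrides the 30-day rule.

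Under section 9 there is no stated route to the dataset.

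**4. Who is affected**

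Residual-disease patients who go on to adjuvant atezolizumab have adverse-event checks at 1 week, 1 month and each of 15 adjuvant cycles, and their 30 days run from the last adjuvant dose. Late effects of the neoadjuvant doses are therefore still collected for them during that time. For objective 3 the gap lies mainly with pCR patients: 18 × 0.30 = 5.4 expected at the design's target rate, 18 × 0.05 = 0.9 at the null rate.

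**5. Size**

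One missed patient is 1 / 18 = 5.6 percentage points on a whole-trial rate.

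**The case against.** The best defense is that the 30-day window followed by related serious events looks deliberate: sections 9.1, 9.4.1 and 9.5.2.6 agree on it. On that view section 3.1 describes clinical care, not data collection, and footnote 7 is a sensible closing check. A visit after day 30 can elicit everything that began before it, and nothing in section 9 bars entry of an event merely because it was elicited late. The same can be said of the pCR 1-month visit.

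Much of this stands. A reader might infer that events after the last adjuvant doses are lost because no adverse-event visit falls inside the 30 days. The documents do not support that, since the first surveillance visit can pick those events up. Nor is late toxicity wholly unrecorded: related serious events and deaths stay reportable, section 9.3.1 requires listed events whether or not they are serious and gives no end date of its own, and chemistry is drawn at each follow-up visit with grade shifts analyzed in Tier 3. Asymptomatic hepatitis may look like an example of a lost event, but section 9.1 keeps laboratory findings without signs or symptoms out of the adverse events at any time, and the chemistry shifts may show them.

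What does not stand is that the documents settle the matter. Section 10.3 belongs to the statistical section, not to clinical care, and has CTCAE documentation at each visit. Footnote 7 and the pCR 1-month visit are not confined to events of earlier onset. Section 10.1 gives no window that would decide between the two readings.

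**Conclusion.** The point holds as a conflict over how long non-serious adverse events are collected. If sections 9.1 and 9.4.1 govern, non-serious immune-mediated events starting more than 30 days after the last dose are under-reported in the toxicity endpoint. For the neoadjuvant safety objective this concerns chiefly pCR patients.

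The amount of under-reporting is unknown, because the documents give no rate of late events. Two stronger readings should be avoided. One is that the trial would report no late toxicity at all; the remaining routes rule that out. The other is to put a size on the loss. A reader might compare the 30 days with the contraception period, "during the treatment period and for 5 months after the final dose of atezolizumab", as if that were the period at risk, but it is a reproductive precaution and is not presented as a window for onset of adverse events. A reader might also apply an assumed event rate to all 18 patients; the plan supplies no such rate, and for objective 3 not all 18 are exposed to the gap.

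This is something that should be corrected. It does not touch the pCR endpoint or the two-stage design.

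**What to change.** Reconcile sections 3.1, 6, 9.1, 9.4.1 and 10.3 so that they give one rule:

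- Keep the 30-day window for adverse events of any cause. In 9.1 and 9.4.1, add that events judged treatment-related or immune-mediated, found at the surveillance visits section 3.1 already requires, are entered in the database whatever their seriousness. Make 10.3 say the same.
- Mark this in the surveillance column of both calendars and amend footnote 7 to match. Say how events found at marked visits after day 30 are handled, including the pCR 1-month visit, and reconcile the 2-year and 3-year surveillance lengths for residual disease.
- State the toxicity analysis window in 10.1, and tabulate events with onset after 30 days separately, by post-surgical pathway.

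This changes recording only: no dose, treatment rule or visit is altered. The cost is wording, slightly more data entry, and possibly a higher reported toxicity rate. Writing the 30-day limit into 3.1 and 10.3 instead would also remove the contradiction, but late non-serious events would stay out of the endpoint and the report would have to say so.
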